4.4.2. Follow-up Assessment

Follow-up assessments will be collected after participants discharged from hospital including 30- day and 90-day active follow-up assessments and one-year passive follow-up assessment.

Thirty Day Follow-up: Participants will be given an appointment for a clinic visit within (+/-) one week after the 30 post-randomization day. Questions regarding symptoms related to MI, other cardiac events, stroke, pneumonia, and wound infection will be asked. If a participant has a readmission prior to the 30-day post-randomization time point, then the electronic medical record, will be reviewed to determine whether the reason for admission includes any of the complications that consist of the primary or other study endpoints, such as coronary revascularization or acute renal failure. If the participant has been admitted to a non-VA hospital, then complete records from this admission will be obtained from that hospital to document the reason for admission and the development of study endpoints leading to readmission. The hospital records obtained will include History and Physical, all consultations, procedures, laboratory values, fluid cultures, copies of EKG and Echocardiography reports, as well as reports from all imaging studies performed, catheterization laboratory reports and operating room reports. To assure access to these records, release of information forms will be signed by the participant as part of the initial informed consent process. If the participant does not present for the follow up within two weeks from the anticipated appointment time, an electronic medical record review and phone call follow-up will be performed and focused questions will be asked, to identify the occurrence of any of the endpoints. Questions about interval readmission will also be asked at the follow up visit/call.

Ninety Day Follow-up: Participants will be given a clinic appointment within two weeks (+ only) after the 90th post-randomization day. Questions regarding symptoms related to cardiac events, stroke, infectious complications will be asked as described above for the 30-day post-randomization follow up. If participants are unable to make the clinic visit within two weeks of the assigned appointment then an electronic medical record review and phone call follow-up will be performed as described above. Readmissions since previous follow-up will also be investigated with similar series of actions as with the 30-day post-randomization follow-up. Pertinent laboratory values (creatinine, troponin), EKG results, cardiac catheterization reports and operating room reports since the previous visit will be reviewed in the electronic medical record to ascertain the presence of coronary revascularization, stroke, MI, or acute renal failure.

One Year Follow-up: Follow up will be performed by trained staff from the Chair's office at twelve months after randomization to ascertain vital status. The CSPCC will generate listings of participants due for follow-up which will be sent to the Chairman's personnel responsible for conducting the telephone interviews. Follow-up data will be obtained by study staff. This removes the need for personal identifying information to be maintained at the individual sites or the CSPCC and helps to protect participant confidentiality. Study participants will be called, chart reviews will be performed, and the VHA Death Ascertainment File (DAF) data will be used to determine a participant's death and date of death. The DAF will be used to assess the one-year vital status of those participants discharged alive from the hospital for whom vital status cannot be determined. Social Security number will be used to obtain the patient identifier PatientICN, which will be necessary for linkage to the DAF. The data collection schedule as shown in Appendix 2.

4.4.3. Safety Assessment

Given the large number of comorbidities expected in the study population and the high-risk operative procedures that these patients will be undergoing, it is anticipated that a large number of AEs will be observed, most of which will not be related to the study intervention. For this reason, the study will only collect reports of Serious Adverse Events (SAEs). Serious adverse events are defined by the ICH for Clinical Safety Data Management (ICH-E2A), the

Food and Drug administration (21CFR312.32) and CSP Global SOP 3.6, as any untoward medical occurrence that:

- Results in death,
- Is life threatening,
- Requires inpatient hospitalization or prolongation of existing hospitalization,
- Results in persistent or significant disability or incapacity,
- Is a congenital anomaly/birth defect, or
- Any other condition that, based upon medical judgment, may jeopardize the subject and require medical, surgical, behavioral, social or other intervention to prevent such an outcome.

SAEs will be identified and documented on the SAE CRF in appropriate medical terminology. The relationship of the SAE to the study intervention involves an assessment of the degree of causality (attributability) between the study intervention and the event. Site investigators will be asked to provide an assessment of relatedness. The assessment provided by the site investigator is part of the information used by the sponsor to determine if the adverse event presents a patient safety concern or requires regulatory reporting. Pursuant to CSP Global SOP 3.6.2, an AE or SAE is deemed to be associated with the use of a study drug/device if “there is a reasonable possibility that the experience may have been caused by the drug/device or by participation in the trial.” Thus, all adverse events with a reasonable causal relationship to the investigational treatment should be considered “possibly related” or “related.” A definite relationship does not need to be established but there must be some evidence to suggest a causal relationship between the investigational treatment and the adverse event (21 CFR 312.32). The following levels of relatedness will be used in this trial:

- Not attributed to a study intervention
- Possibly attributed to a study intervention
- Attributed to a study intervention.

All SAEs, whether related or unrelated to the treatment interventions, will be recorded and reported in an expedited fashion. Assessment of relatedness for SAEs is described above. Unexpected serious adverse events that are attributed or possibly attributed to a study intervention will be managed as provided in CSP Global SOP 3.6. Directions on how to

complete the Serious Adverse Event Form will be detailed in the Operations Manual. Sites are required to report each SAE to the Sponsor within 3 calendar days from the time the site investigator becomes aware of it. The PCC Study Pharmacist will complete a safety and regulatory review of all SAEs. All investigators will be notified of any new hazards or other trends involving patient safety as provided in Global SOP 5.3. Active monitoring of reportable SAEs will begin as soon as the participant is randomized and will continue until the participant's 90th post-randomization day. The treatment plan includes follow-up outpatient visits of all patients for 3 months after randomization.

4.5. Sample Size Consideration

The sample size estimation and power analysis are based on the hypothesis testing of the primary composite endpoint of all-cause post-randomization mortality, myocardial infarction (MI), coronary revascularization, acute renal failure, or post-randomization stroke up to 90 days after randomization. The primary hypothesis of the study is that in VA patients with high cardiac risk undergoing a surgical procedure, a significantly smaller proportion of participants receiving blood under a liberal transfusion strategy will experience the composite endpoint compared to participants under restrictive transfusion strategy at 90 days after randomization. The primary analysis will be done as an "intent-to-treat" analysis. Our database review revealed that 29.8% out of 25,343 patients in the VA population who were at high cardiac risk and had nadir postoperative Hb range between 6-9 gm/dl developed the composite endpoint of death, MI, acute renal failure, or coronary revascularization within 90 days from the index operation. Based on the analysis, a baseline event rate of 30% for the composite endpoint is expected in the restrictive group. We also assume a 25% reduction or 22.5% event rate in the liberal group. To detect the expected 7.5 percentage point difference or 25% reduction, a sample size of 1444 will be required at 90% power, 5% type-I error rate and with a two-sided test (Appendix 3). Assuming 5% dropout rate, then 1520 participants (or 760/group) will be needed to achieve the desired testing power.

5. GENERAL ANALYSIS CONSIDERATIONS

5.1. Timing of Analysis

The Study Group, which consists of all participating investigators and study coordinators, will meet annually to discuss the progress of the study and any problems encountered during the conduct of the trial. This group will be provided a report prior to meetings. The information provided will include data on:

- Screening, Enrollment, and Retention
- Participant background characteristics at entry
- Data quality and protocol adherence

The groups charged with monitoring the various aspects of the study will be the Executive Committee, the Data Monitoring Committee (DMC), and the VA's Central IRB. These committees will meet at regular intervals according to the current Cooperative Studies Program guidelines: prior to the beginning of participant intake and at least every twelve months thereafter.

The final analysis will be performed after the data collection phase of the study is complete and the data are cleaned and locked per CSP SOPs and after the finalization and approval of this SAP document.

5.2. Missing Data and Imputations

Every effort will be made to minimize the occurrence of missing data, particularly for the primary and main secondary outcome measures. For the primary outcome, every effort will be made to contact participants until subject termination. In the event of a potential drop out, every effort will be made to capture the primary outcome data from the VA databases. For participants who drop out during the study multiple imputation (MI) method may be used for certain endpoint analyses. Multiple imputations will be based on Rubin's procedure using SAS PROC MI and PROC MIANALYZE when missing is at random. Sensitivity analysis will be performed to compare the results from the imputed data and the complete data without imputation.

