Other Analyses 1. Baseline characteristics 2. Disposition status 3. Adherence 4. Age of Blood in relation to 90 day composite endpoint, wound Infection, and pneumonia 5. Time-to-event analyses for primary and secondary endpoints	1. Student t or Wilcoxon test, Pearson chi-square or Fisher test, 2. Pearson chi-square test 3. Pearson chi-square test 4. Pearson chi-square tests and Logistic regression 5. Log-rank test and Cox regression	1. PROC TTEST, PROC FREQ, PROC NP1WAY 2. PROC FREQ 3. PROC FREQ 4. PROC FREQ, PROC GENMOD 5. PROC LIFETEST, PROC PHREG

F. Criteria for Study Termination

There will be three interim analysis of the primary outcome measure performed in the study when 25%, 50%, 75% of the planned participants completed their participation in the study. If analysis of the primary outcome rates at the time of interim analysis indicates that the null hypothesis can be rejected the study will be recommended for termination for safety reasons.

G. Handling of Missing Data

Every effort will be made to minimize the occurrence of missing data, particularly for the primary and main secondary outcome measures. For the primary outcome, every effort will be made to contact the participants over the phone until participant termination. In the event of a potential drop out, every effort will be made to capture the primary outcome data from the VA databases. For participants who drop out during the study, multiple imputation (MI) method may be used for certain endpoint analyses. Multiple imputations will be based on Rubin's procedure using SAS PROC MI and PROC MIANALYZE. Sensitivity analysis will be performed to compare the results from the imputed data and the complete data without imputation.

H. Reporting of Any Deviations from the Original Statistical Plan

A more detailed statistical analysis plan (SAP) will be generated which will include the details of each statistical analysis plan for each outcome measure along with the suggested table shells for any reports that will be produced during the study and at the end of the study. Any deviations in the statistical plan from the protocol will be specified in the SAP. Any deviations from the SAP will be specified in a revised main manuscript which will be prepared and published at the end of the study.

XVII. STUDY ORGANIZATION AND ADMINISTRATION

A. Requirements for Participating Medical Centers

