7.1. Primary Endpoint Analysis

The primary study endpoint will be a composite outcome of all-cause mortality, MI, coronary revascularization, acute renal failure, or post-randomization stroke within 90 days from randomization. A clinical events committee will adjudicate all component events for the primary endpoint. The number and percentage of participants with the composite endpoint at the 90-day visit after the randomization will be summarized and compared according to assigned transfusion strategy (analysis by intent to treat) using Pearson χ^2 test. Another analysis will compare primary endpoint between the two transfusion strategies stratified by clinical sites using the Cochran-Mantel-Haenszel test (Table 16a-e). The test for differences between transfusion strategies in the primary outcome will be conducted at an overall α -level of 0.05. Additional analysis will be conducted using logistic models to adjust for other clinical factors, such as age, RCRI, and nadir Hb. The interactions of the intervention with age, RCRI and nadir Hb will also be considered.

Odds ratio and 95% confidence interval (CI) will be presented using SAS PROC GENMOD or PROC LOGISTIC. Assumptions of the model including linearity in the logit of the composite event risk for continuous variables will be checked. We will assess goodness-of-fit using the statistic -2 log likelihood, which has a chi-square distribution under the null hypothesis that all the explanatory variables in the model are not associated with the outcome

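### The single planned missing-data check compares two analyses that make no allowance for outcomes missing not at random, so their agreement would say little about whether drop-out could change the primary conclusion

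*SAP*

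**What the plan says.** SAP 5.2 and protocol XVI.G share the same core text. Sites try to avoid missing outcomes and search VA databases for people who may drop out. After that, "multiple imputation (MI) method may be used for certain endpoint analyses". The SAP adds a condition that the protocol lacks: imputation is run with "PROC MIANALYZE when missing is at random". Both then name one robustness check: "Sensitivity analysis will be performed to compare the results from the imputed data and the complete data without imputation".

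The primary endpoint is "compared according to assigned transfusion strategy (analysis by intent to treat) using Pearson χ^2 test" (SAP 7.1). ITT keeps every randomized participant in the analysis whether or not they complete (SAP 5.4). Neither document says how an unknown 90-day status enters the chi-square test, names the imputation model, or lists the endpoints to be imputed.

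The sample size allows for loss: "Assuming 5% dropout rate, then 1520 participants (or 760/group) will be needed to achieve the desired testing power" (SAP 4.5).

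**The concern.** A missing-data sensitivity analysis should change the assumption that cannot be verified and show whether the conclusion survives. Here that assumption is that participants with unknown outcomes resemble comparable participants whose outcomes are known. Imputation under missing at random relies on it, and so does dropping the unknowns, in an equal or stronger form. Comparing the two never relaxes it.

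Nothing else in the plan does so. The Completers population (SAP 5.4) is another complete-case analysis. The Kaplan-Meier and Cox analyses (SAP 7.4) state no provision for informative censoring. No delta-adjusted, pattern-mixture, best/worst-case or tipping-point analysis appears in either document.

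Illness-related loss is plausible from the documents. Termination reasons in SAP Table 6 include a serious adverse event other than death, voluntary withdrawal and administrative termination. The stake is that a result that depends on the unknown outcomes and one that does not could both be reported as robust.

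**Working it through.** **Inputs (SAP 4.5).** Restrictive rate: "a baseline event rate of 30% for the composite endpoint is expected in the restrictive group". Liberal rate: "We also assume a 25% reduction or 22.5% event rate in the liberal group". Size: "a sample size of 1444 will be required at 90% power, 5% type-I error rate and with a two-sided test". Drop-out is 5%.

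**The plan's own figure.** With pooled variance and no continuity correction, n per arm = [1.960·√(2·0.2625·0.7375) + 1.282·√(0.225·0.775 + 0.30·0.70)]² / 0.075² = 721.2, rounded up to 722. The total is 1,444, and 1,444/0.95 = 1,520. Both stated figures reproduce. The allowance is 1,520 − 1,444 = 76 people, or 38 per arm if split equally (an assumption).

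**Test used.** Z = (p_R − p_L)/√(p̄(1 − p̄)(1/n_L + 1/n_R)), whose square is the Pearson chi-square. Observed data use 722 per arm; filled-in data use 760.

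**Two starting points**
- Design-size: 163 vs 217 of 722 (22.6% vs 30.1%), Z = 3.23, p = 0.001.
- Borderline: 183 vs 217 of 722 (25.3% vs 30.1%), Z = 2.00, p = 0.046. At 184 vs 217 significance is already gone (p = 0.053).

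**What the planned check would show.** Assume imputation within arm from that arm's observed rate, combined by Rubin's rules. The imputed analysis then gives Z of about 3.2 and 2.0, essentially the complete-case values, whatever the drop-outs' true outcomes.

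**What a tipping-point analysis would show.** Hold restrictive drop-outs at about their arm's rate, 11 of 38, so the restrictive arm has 217 + 11 = 228 of 760. Then raise the events among the 38 liberal drop-outs.

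| Start | Liberal drop-outs with events | Filled-in events | Z | p |
|---|---|---|---|---|
| Design-size | 17 (45%, twice the arm's rate) | 180 vs 228 | 2.78 | 0.006 |
| Design-size | 30 (79%) | 193 vs 228 | 2.01 | 0.045 |
| Design-size | 31 (82%) | 194 vs 228 | 1.95 | 0.051 |
| Borderline | 10 (26%) | 193 vs 228 | 2.01 | 0.045 |
| Borderline | 11 (29%) | 194 vs 228 | 1.95 | 0.051 |

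In the borderline case the arm's own rate predicts 0.253 × 38 = 9.6 events, so one or two extra are enough.

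**Sensitivity to rounding.** Starting from 162 liberal events and filling restrictive drop-outs at exactly 30.1% moves the tipping points to 33 of 38 (87%) for the design-size result and, from 183 events, 12 of 38 (32%) for the borderline one.

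**Outer bounds at the design-size result.** All liberal and no restrictive drop-outs with events: 201 vs 217, Z = 0.92. The reverse: 163 vs 255, Z = 5.28. These are limits, not predictions.

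**Between the extremes.** In simulation at the design rates, the share of significant trials that turn non-significant is about 10% if drop-out event rates are 45% liberal vs 30% restrictive, and about 22% if they are 60% vs 30%.

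These fill-ins ignore imputation variance, so real tipping points would come slightly earlier.

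**The case against.** The case for leaving the plan alone has several parts, and much of it stands as a limit on the size of the problem.

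- **Drop-out is not the same as an unknown outcome.** Record review and phone calls replace missed visits, and non-VA admission records are obtained (protocol VI and IX.C.2). Death-file data are to be requested for all randomized participants. In Table 2 of the protocol, deaths are 15.3 of 29.5 percentage points, about half of composite events. This stands: 38 per arm is an upper bound. Retrieval shrinks the unknown group but does not test assumptions about those who remain in it.
- **The design-size result is sturdy.** This stands: 82% of liberal drop-outs would need events.
- **Imputed and complete-case results could differ.** A model using in-hospital or 30-day data might separate them. This stands in part, because the close agreement shown above assumes same-arm imputation and the SAP names no model. A richer model would still assume missing at random.

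Two stronger readings are tempting. One sets 76 missing against the 34-event margin on 722 per arm (173 vs 207, Z = 2.03; 174 vs 206 gives 1.91) and infers that the missing outweigh the margin more than twofold. With 38 missing per arm, the between-arm difference can move by at most 38 in either direction, so the comparison is 38 with 34. The other infers, from unblinded physicians, that drop-out will be informative by arm. Participants, who make the refusals, and the Endpoint Committee are blinded to allocation (SAP 4.1, 4.3). The documents do not support that inference.

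**Conclusion.** The point holds as a gap in what the plan can show. The documents do not support a claim that 5% drop-out would overturn the result, or that the imputed and unimputed analyses must agree under every model. The planned comparison leaves the assumption that matters unvaried, so agreement could not separate a result that survives until 82% of liberal drop-outs have events from one that fails at 29%.

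Those figures rest on an equal split of the allowance, all 38 outcomes per arm staying unknown, restrictive drop-outs at about their arm's observed rate, and single-value fill-in. With fewer unknowns the result would be harder to overturn. The primary test can still be run. What is lacking is support for any statement that it is robust to missing outcomes, and this should be settled before database lock.

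**What to change.** In SAP 5.2:

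1. State how an unknown 90-day status enters the primary chi-square test.
2. Commit to a named imputation model for the ITT primary endpoint, in place of the present optional wording.
3. Replace or supplement the imputed-versus-unimputed comparison with a two-way, delta-adjusted tipping-point analysis. Vary the event rate among missing outcomes separately in each arm, and report the smallest departure that changes the conclusion.
4. Use death-file vital status where consent permits, so that mainly the non-fatal components are imputed. First reconcile protocol IX.C.2.c, which requests death data for everyone randomized, with IX.D.2, which ends participation for those refusing active follow-up and does not collect one-year mortality from those declining long-term follow-up. Carry any remaining unknown deaths into the tipping-point analysis.

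The cost is one extra paragraph and one table. The tipping-point analysis itself needs no new data collection; how far death-file data can be used depends on the reconciliation in step 4.

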5.3. Analysis Conventions

This section details general policies to be used for the statistical analyses. Departures from these general policies may be given in the specific detailed sections of this statistical analysis plan. When this situation occurs, the rules set forth in the specific section take precedence over the general policies. The following policies will be applied to all data presentations and analyses.

All statistical tests will use a significance level of $\alpha = 0.05$ unless otherwise specified. Two-tailed tests will be performed for all analyses that use statistical testing.

All p-values will be rounded to 3 decimal places. All p-values that round to 0.000 will be presented as ‘<0.001’ and p-values that round to 1.000 will be presented as ‘>0.999’. Any p-value $\leq \alpha$ will be considered statistically significant.

Summary statistics will consist of the number and percentage of responses in each category for discrete variables, and the mean, median, standard deviation (SD), minimum, and maximum for continuous variables.

All mean and median values will be formatted to one more decimal place than the measured value. Standard deviation values will be formatted to two more decimal places than the measured value.

All percentages will be rounded to one decimal place. The number and percentage of responses will be presented in the form XX (XX.X), where the percentage is in the parentheses. The decimal of the percentage may be dropped due to space constraints when creating a table.

All listings will be sorted for presentation in order of intervention group, site number, subject number, and date of procedure or event.

All analysis and summary tables will have the population sample size for each intervention group in the column heading.

Calculating change from baseline to a visit will be done as follows: change = visit – baseline.

Unless otherwise specified, baseline is defined as the last data point before the participant is randomized.

Version 9.4 of SAS® or higher will be the statistical software package used to produce all summaries, listings, statistical analyses, and graphs.

Updated version of MedDRA will be used for adverse event and pre-intervention coding.

